Fractional flow reserve (FFR), coronary flow reserve (CFR) and the index of microcirculatory resistance (IMR) will be the primary physiological indices recorded

**Exploratory Objectives:** To compare the incidence of peri-PCI myonecrosis with OAS versus RA, as assessed by measurement of CK-MB and Troponin I and in a subgroup of 20 myocardial edema and late gadolinium enhancement on cardiac MRI..

**Rationale:** Lower incidence of microvascular compromise with OAS may be protective against peri-atherectomy microvascular “plugging” and loss of tissue perfusion, and thereby may result in a reduction in peri-PCI myocardial necrosis, potentially protecting left ventricular function. In patients undergoing elective PCI, IMR has been shown to

independently predict PCI-related microvascular damage and peri-procedural myonecrosis.

**Trial Design:** Randomized, prospective, single-center, investigator initiated, study at Columbia University Medical Center (CUMC).

**Sample Size:** 20

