### Procedures:

**Physiological indices:** Subjects will be randomized on a 1:1 basis to OAS versus RA. In both groups, we will perform sequential physiological interrogation of the coronary vasculature before and immediately after atherectomy and at the end of PCI, utilizing a direct and robust assessment of microvascular function. This will be achieved by measurement of the mean transit time ( $T_{mn}$ ) of saline using a single pressure-temperature sensor-tipped coronary wire (Certus™ guidewire, St Jude Medical, St Paul, Minnesota). The following parameters will be assessed:

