#### (5) FFR ( $P_d/P_a$ at hyperemia)

where  $P_a$  is the aortic pressure measured by the guiding catheter at peak hyperemia. PCI is indicated in stenoses with FFR <0.8.

$T_{mn}$  under basal condition followed sequentially by IMR, FFR and CFR under maximum hyperemia will be measured at 3 separate time points: 1) pre-atherectomy, 2) immediately post atherectomy and 3) at the end of the PCI.

	Screening	Procedure	Post Procedure	Discharge
Consent	X			
Medical History	X			
Randomization	X			
CK/MB			X 	
Troponin I			X 	
Physiological Measurements (FFR)		X 		

X 4-8 hours post procedure; if positive again at 12-18 hours

X Physiological measurements (Total coronary flow, Microvascular resistance, Coronary wedge pressure, Coronary flow reserve and Fractional flow reserve) will be taken before and immediately after atherectomy and at the end of PCI)

**Sample Size:** A clinically important difference would be 20% reduction in IMR in OAS, equating to an IMR difference of 7 (SD=8,  $\alpha$  =0.05 and power=0.80) and requiring a total sample size of 20.

**Projected time for completion:** 1 year. CUMC has a large volume for PCI with ~ 3000 number of PCIs per year including ~250 procedures requiring atherectomy.

**Significance of the results:** If OAS is shown to cause lower disruption and loss of coronary microcirculatory function, the use of this atherectomy device may have significant favorable impact on myocardial recovery and function post PCI as compared to RA, potentially leading to prevention of major adverse cardiovascular events.

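### Peri-PCI myonecrosis is to be compared as an incidence with about 10 patients per arm; comparing the CK-MB and troponin I levels already drawn would be more efficient at almost no cost.

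*Combined protocol and SAP*

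**What the plan says.** The Exploratory Objectives paragraph sets out "To compare the incidence of peri-PCI myonecrosis with OAS versus RA, as assessed by measurement of CK-MB and Troponin I". The same sentence adds imaging: "in a subgroup of 20 myocardial edema and late gadolinium enhancement on cardiac MRI".

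The size is given as "Sample Size: 20", and under Procedures "Subjects will be randomized on a 1:1 basis to OAS versus RA", so about 10 patients per arm.

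The footnote to the schedule table, at the end of section (5) FFR, times both markers: "4-8 hours post procedure; if positive again at 12-18 hours". The table marks them in the post-procedure column only, with no entry at screening or during the procedure. NSTEMI is an accepted indication under Inclusion Criteria.

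The documents give no cut-off for a positive marker, no expected incidence, no test and no planned analysis of marker levels. The only power statement concerns IMR.

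**The concern.** CK-MB and troponin I come back from the laboratory as concentrations. Counting only who crosses a line treats a patient just above it like one far above it. With about 10 patients per arm, an outcome such as 2/10 vs 4/10 says very little, and if nearly all or nearly no patients are positive the count cannot separate the arms.

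The protocol's rationale runs from microvascular plugging to myocardial necrosis, and these markers are one of its two measures of that injury. A null incidence result could be misread as showing no difference in myonecrosis, and the estimate passed on to a later trial would be less precise than the same blood samples allow. With no cut-off stated, the incidence also depends on a line that could be drawn after the data are seen.

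**Working it through.** **Plan's own figure.** None is given for myonecrosis. The total of 20 comes from the IMR calculation (difference 7, SD 8, alpha 0.05, power 0.80). The usual formula gives n per arm = 2 × (1.960 + 0.842)² × (8/7)² = 20.5, so 21 per arm and 42 in total (two-sided). One-sided, it is 2 × (1.645 + 0.842)² × (8/7)² = 16.2, so 17 per arm and 34 in total. Neither gives 20 in total. I therefore use 10 per arm as stated and repeat the check at 20 per arm.

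**Assumptions.** Incidences are assumed, because the documents give none. The log-marker is taken as normal with equal SD in both arms, so incidences p1 and p2 imply a standardized shift d = Φ⁻¹(p2) − Φ⁻¹(p1). Tests are two-sided at 0.05.

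**Step 1: information kept after dichotomizing.** For a normal marker and a small shift, the fraction kept is φ(z)²/[p(1−p)], with z = Φ⁻¹(p).

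| Incidence p | 10% | 20% | 30% | 50% |
|---|---|---|---|---|
| Kept | 34% | 49% | 58% | 64% |

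The function is symmetric, so 90% behaves like 10%. At the average incidence of the three contrasts below (45%, 35%, 50%) it keeps 63%, 60% and 64%, a loss of about 36-40%. Ten patients per arm analysed as yes/no are then worth about six per arm analysed as levels.

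**Step 2: what a binary result must look like.** By Fisher's test at 10 per arm, 0 vs 4 gives p = 0.087 and 0 vs 5 gives 0.033; 2 vs 7 gives 0.070 and 2 vs 8 gives 0.023. Boschloo's test, which also controls type I error and is less conservative, gives 0.042 for 0 vs 4 and 0.041 for 2 vs 7.

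**Step 3: power at 10 per arm.** Binary power is by exact enumeration of the two binomials. Rank-test power is from 4,000 simulated trials and moves by a point or two between runs.

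| Contrast | d | Fisher | Boschloo | Rank test | t-test on log level |
|---|---|---|---|---|---|
| 30% vs 60% | 0.778 | 12% | 25% | 34% | 38% |
| 20% vs 50% | 0.842 | 13% | 25% | 38% | 43% |
| 30% vs 70% | 1.049 | 24% | 42% | 55% | 60% |

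If OAS halves the incidence, the order is the same at lower power. From 20%, 30%, 40% and 50%, Fisher has 1%, 3%, 6% and 9%; Boschloo 5%, 9%, 13% and 18%; the t-test 15%, 19%, 24% and 30%. At a high incidence (80% vs 95%) the figures are 2%, 7.5% and 40%.

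**Step 4: limits of the level analysis.** At 10 per arm a t-test reaches 80% power only for a shift of about 1.32 SD. The 95% interval for the difference has half-width 2.101 × √(2/10) = 0.94 SD.

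**Step 5: if 20 per arm was meant.** For the same three contrasts Fisher has 35%, 41% and 60%, Boschloo 45%, 49% and 70%, and the t-test 67%, 74% and 90%. The level analysis is still the stronger one.

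**Step 6: which draw to use.** The 4-8 hour sample is the only one scheduled for everyone. The 12-18 hour sample is taken only after a positive first result, so a peak of available values would be measured differently according to outcome.

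**The case against.** **No power is promised.** The objective is labelled exploratory, and the power statement covers IMR only. A reader might infer that the design fails a claim it made; it makes none here. This stands, and it makes the point one of efficiency.

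**The loss depends on the unknown incidence.** A reader might infer that dichotomizing throws away most of the information. The documents give no incidence to support that: it holds at about 20% or below and at correspondingly high rates, but near the middle more than half is kept. What stands is a loss of roughly two fifths at best, and more elsewhere.

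**Part of the power gap comes from the binary test chosen.** Against Fisher, a level analysis looks two to three times as powerful. The plan names no test, and against Boschloo the gain is about 1.3 to 1.7 times (for example 34/25 and 43/25). The smaller range is the fair one.

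**Markers are not the only injury measure.** The same sentence names MRI edema and late gadolinium enhancement, in a subgroup as large as the whole stated sample. A reader might infer that the link to injury rests on the markers alone; it does not.

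**Levels are not excluded.** The wording refers to measuring the two markers and specifies no test. The plan fails to plan a level analysis; it does not forbid one.

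**Levels carry pre-procedural elevation.** No baseline draw is scheduled, NSTEMI patients are eligible, and dialysis patients are not excluded by the renal criterion. In arms of 10, one or two such patients could dominate a geometric mean, and the equal-SD normal assumption may fail. This is the most serious objection. It affects incidence as well, since a patient positive beforehand counts as an event, so it is a reason to prefer ranks and a sensitivity analysis, not to keep the count.

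**Conclusion.** The point holds as a cheap improvement in efficiency. The plan states an incidence comparison with about 10 patients per arm where levels are already scheduled. Under a normal log-marker with equal SD, dichotomizing loses about 36-40% of the information at mid-range incidences and more towards either extreme. In the three main contrasts, power rises from 12-24% (Fisher) or 25-42% (Boschloo) to about 34-60% with levels.

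These sizes rest on assumed incidences and on the distributional assumption; a mixture of patients with and without pre-procedural elevation would reduce the gain by an amount the documents do not allow one to estimate. The ordering of the methods is unchanged at 20 per arm.

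A reader might also infer that analysing levels would make the comparison adequately powered. It would not. Either result should be read as an estimate with a wide interval, and a null finding as inconclusive.

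**What to change.** Reword the exploratory objective so that the between-arm comparison is of CK-MB and troponin I levels at the 4-8 hour draw.

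- Report a rank-based shift with its 95% CI as the preferred analysis, or a geometric mean ratio with 95% CI. Ranks are less exposed to one or two extreme values.
- State the cut-off for a positive marker before data are seen, and report incidence descriptively against it.
- Do not use the peak of available values.
- Where a pre-procedure marker value already exists in the record, use it as a covariate.
- Add a sensitivity analysis excluding NSTEMI patients. This is a pre-randomization characteristic, so the exclusion keeps the comparison between randomized groups.
- Say that the comparison is exploratory and that a null result is not evidence of no difference.

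The cost is a reworded sentence and a few lines of analysis text, with no new patients or samples. The price is some remaining noise from pre-procedural elevation, which only a baseline draw in every patient would address; that would be an added sample and a separate decision. The stated total of 20 should also be reconciled with its own inputs, but this change does not depend on it.

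### The MRI subgroup of 20 is as large as the whole stated trial, and the MRI has no entry or time point in the schedule

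*Combined protocol and SAP*

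**What the plan says.** The Exploratory Objectives compare peri-PCI myonecrosis between orbital (OAS) and rotational (RA) atherectomy by CK-MB and Troponin I, and "in a subgroup of 20 myocardial edema and late gadolinium enhancement on cardiac MRI". The synopsis then states "Sample Size: 20". The Sample Size paragraph after the schedule table repeats this as "requiring a total sample size of 20", and the Procedures section sets 1:1 allocation.

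The schedule table has rows for consent, medical history, randomization, CK/MB, Troponin I and the invasive physiological measurements. The biomarker footnote reads "4-8 hours post procedure; if positive again at 12-18 hours". The other footnote lists the five invasive indices. Neither mentions MRI, and nothing is marked under Discharge. The Procedures text describes no MRI. The Risks section discusses MRI, including dye reactions and claustrophobia, but gives no number, timing or selection rule.

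The Inclusion Criteria admit patients with NSTEMI. The General Exclusion Criteria bar STEMI within 24 hours of first presentation but do not exclude earlier infarction.

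**The concern.** A subgroup is normally smaller than the trial it comes from. Here the two have the same size, and the text does not say whether all patients are scanned or whether one number is wrong. The reader therefore does not know the planned MRI sample. If a true subset is meant, nothing says how patients enter it or whether they are chosen before the device is known. Choosing them after assignment could bias the comparison of devices.

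With no schedule entry, there is no defined time for the scan, and staff who followed the schedule literally would not collect it.

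The interpretation is also open. The objective concerns injury around the PCI, yet some patients may arrive with a recent infarct that itself produces edema and enhancement. With no pre-procedure scan specified, the plan gives no means of separating the two.

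**Working it through.** **1. Subgroup against total.** The MRI number is 20 (Exploratory Objectives) and the total is 20 (synopsis and Sample Size paragraph). The ratio is 20/20 = 100%.

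**2. Does the total follow from its own inputs?** This matters because the total is the denominator of the MRI subgroup. The inputs, all from the Sample Size paragraph, are "equating to an IMR difference of 7", SD = 8, and alpha and power of "0.05 and power=0.80". Allocation is from Procedures: "Subjects will be randomized on a 1:1 basis to OAS versus RA". Sidedness is not stated, so both are shown.

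For two independent means, n per arm = 2 × (z_alpha + z_power)² × SD² / difference².

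- Two-sided: 2 × (1.960 + 0.842)² × 64/49 = 20.5, so 21 per arm and **42 in total**. The t-test version gives 21.5, so 22 per arm and 44 in total.
- One-sided: 2 × (1.645 + 0.842)² × 64/49 = 16.15, so 17 per arm and **34 in total**. The t-test version gives 16.9, so also 17 per arm.

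The stated total of 20 is not reproduced. With 10 per arm, the difference divided by its standard error is 7 / (8 × √(2/10)) = 1.96. Power is then about 0.50 two-sided (0.46 by t-test) or 0.62 one-sided (0.59 by t-test), against the stated 0.80.

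**3. What this does to the subgroup.** With a total of 42, a subgroup of 20 is 20/42 = 48% of patients. With 34 it is 20/34 = 59%. In either case the word subgroup would make sense. The MRI number therefore cannot be settled apart from the total.

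**4. Where MRI appears.**

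| Place | MRI mentioned? |
|---|---|
| Exploratory Objectives | Yes, with the number 20 |
| Procedures | No |
| Schedule table and both footnotes | No |
| Risks | Yes, without number, timing or selection |

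**5. Attribution.** NSTEMI is an accepted indication, and no scan before the procedure is specified. CK/MB and Troponin I are marked only after the procedure, so the scheduled biomarkers do not supply a baseline either. Because earlier infarction is not excluded, enhancement from old scar is possible even in patients without NSTEMI at entry.

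**The case against.** Several things can fairly be said for the plan.

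- **Scanning 20 of 20 is possible.** A reader might infer that the two numbers are arithmetically impossible together. They are not. If all patients are scanned, the objective is workable and only the word subgroup is wrong. The documents support a conflict of wording and numbers, and no more.
- **The MRI was intended.** A reader might infer from the schedule that no scan would be done. The stated objective and the Risks text show otherwise, so this is an omission. A row lost in the conversion from PDF cannot be fully excluded, but the footnotes and the Procedures text also lack MRI.
- **The total may be the wrong number.** A reader might conclude that 20 was meant per arm, which would make a subgroup of 20 coherent. The result of 20.5 per arm invites that reading, but the documents say total. Another route also leads to 20: a one-sample formula with the same inputs gives 10.25, or roughly 10 per arm. The origin of the figure cannot be recovered from the text.
- **Restricting by NSTEMI solves attribution only in part.** This is correct, because old scar may remain. The number of scans is also not stated, so the problem depends on there being no scan before the procedure. A paired baseline scan would deal with attribution more fully, but it adds a scan for every patient in the MRI comparison. Separate reporting is the cheaper step.

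None of this removes the need to reconcile the numbers and state the time point.

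**Conclusion.** The point holds as a conflict between two stated numbers together with a missing schedule entry. The MRI subgroup is 100% of the stated total, and that total does not follow from its own inputs, which give about 42 two-sided or 34 one-sided. Those figures assume a comparison of two independent groups at 1:1, with no allowance for dropout. The documents do not show which number is in error.

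The attribution problem holds to the extent that NSTEMI patients are enrolled and no pre-procedure scan is made. The documents give no expected share of NSTEMI patients, so its size cannot be stated.

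As an MRI matter this is minor, because the objective is exploratory. The shortfall in the total also affects the main IMR comparison, and it is used here only because it fixes the denominator of the subgroup.

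**What to change.** 1. Reconcile the MRI number and the total in one step with the sample-size calculation, and state whether that calculation is one- or two-sided.
2. State either that all randomised patients are scanned, or that a defined subset is scanned, giving its size and a selection rule fixed before the device is assigned.
3. Add an MRI row with its time point to the schedule.
4. Report edema and late gadolinium enhancement separately by NSTEMI at entry. Base any statement about peri-PCI injury on patients without NSTEMI, and note that older scar may remain because prior infarction is not excluded.

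Items 2 and 3 cost some wording, one table row and, if a subset is chosen, a selection rule. Item 4 changes the analysis population, so the attributable comparison rests on fewer patients; it alters no patient's care. Item 1 may cost more: if the inputs are kept, enrolment rises from 20 to about 42 (34 one-sided). If the total of 20 is kept, the stated power or inputs must change.

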**Inclusion Criteria:**

- 1) Age  $\geq$  18 years
- 2) Patient with an indication for PCI including:
  - i) Angina (stable or unstable),
  - ii) Silent ischemia (a visually estimated target lesion diameter stenosis of  $\geq 70\%$ , a positive non-invasive stress test, or FFR  $\leq 0.80$  must be present),
  - iii) NSTEMI
- 3) Patients will undergo cardiac catheterization and possible or definite PCI with intent to stent using any non-investigational metallic drug-eluting stent (DES)
- 4) Signed written informed consent
- 5) Heavily calcified (severe) lesions necessitating atherectomy.

**Angiographic inclusion criteria:**

- 1) The target lesion must be located in a native coronary artery with visually estimated reference vessel diameter of  $\geq 2.25$  mm to  $\leq 4.00$  mm.
- 2) Lesion length between 20 mm and 50mm

**General Exclusion Criteria:**

- 1) Estimated creatinine clearance  $<30$  ml/min using Cockcroft-Gault equation, unless the patient is on dialysis;
- 2) STEMI within 24 hours of initial time of presentation to the first treating hospital, whether at a transfer facility or the study hospital.
- 3) PCI within 24 hours preceding the study procedure.
- 4) Cardiogenic shock (defined as persistent hypotension (systolic blood pressure  $<90$  mm/Hg for more than 30 minutes) or requiring pressors or hemodynamic support, including IABP, at time of procedure.
- 5) Mobitz II second degree or complete heart block
- 6) Malignant ventricular arrhythmias requiring treatment
- 7) Pulmonary edema defined as patient with shortness of breath, evidence of volume overload on physical exam, and crepitations on physical exam ( $>1/3$  of lungs) or radiographic interstitial or alveolar pulmonary edema
- 8) Subject is intubated.
- 9) Known LVEF  $<35\%$ .
- 10) Severe valvular disease (e.g. severe mitral regurgitation or severe aortic stenosis)
- 11) Patient is participating in any other investigational drug or device clinical trial that has not reached its primary endpoint.
- 12) Women who are pregnant or breastfeeding (women of child-bearing potential must have a negative pregnancy test within one week before treatment).

**Angiographic Exclusion Criteria:**

- 1) Lesion length  $<20$  mm
- 2) Study target lesion in a bypass graft
- 3) Ostial RCA study target lesion
- 4) Chronic total occlusion (TIMI flow 0/1) study target lesion
- 5) Bifurcation study lesion with a planned dual stent strategy
- 6) In-stent restenosis study target lesion

### Procedures:

**Physiological indices:** Subjects will be randomized on a 1:1 basis to OAS versus RA. In both groups, we will perform sequential physiological interrogation of the coronary vasculature before and immediately after atherectomy and at the end of PCI, utilizing a direct and robust assessment of microvascular function. This will be achieved by measurement of the mean transit time ( $T_{mn}$ ) of saline using a single pressure-temperature sensor-tipped coronary wire (Certus™ guidewire, St Jude Medical, St Paul, Minnesota). The following parameters will be assessed:

#### (1) Total coronary flow ( $1/T_{mn}$ )

With the pressure sensor of the coronary wire acting also as a distal thermistor and the shaft of the wire serving as a proximal thermistor, the mean transit time of saline injected down a coronary artery can be derived from a coronary thermodilution curve. De Bruyne, Pijls and colleagues found a strong correlation between the inverse of  $T_{mn}$  and absolute flow.

#### (2) Microvascular resistance ( $P_d * T_{mn}$ )

Extrapolating from Ohm's law, distal coronary pressure ( $P_d$ ) divided by the inverse of the hyperemic mean transit time (a correlate to absolute flow), measured simultaneously with the coronary pressure wire, will evaluate microvascular resistance. Under peak hyperemia (achieved by intravenous infusion of adenosine at 140  $\mu$ g/kg/min) this ratio has been called the IMR^3. IMR is derived from the assumption that at peak hyperemia the variability of resting vascular tone and hemodynamics will be eliminated, and the *minimum* microvascular resistance will be achieved.

#### (3) Coronary Wedge Pressure ( $P_w$ )

In addition to the IMR we will assess the coronary wedge pressure, measured by trapping the pressure transducer on the pressure wire with a proximally inflated balloon. Measurements will be taken immediately following atherectomy and then repeated following administration of adenosine and a 3 minute rest period. The difference between the pre and post adenosine coronary wedge pressure will be indicative of the microcirculatory "plugging" caused by atherectomy.

In addition, we will measure  $T_{mn}$  both at rest and at peak hyperemia. If the effects of OAS on the microvasculature are less than RA and the relatively smaller microparticles generated by OAS are more readily "washed out" of the microcirculation with adenosine-induced hyperemia, we expect to see a difference between OAS and RA in  $T_{mn}$  and  $P_d * T_{mn}$  both with resting and hyperemic (i.e. IMR) indices.

We will also use the data to calculate the coronary flow reserve (CFR) that is an index of total blood flow in coronary bed under peak hyperemia relative to rest as described previously.

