# **Comparison of Orbital versus Rotational Atherectomy Effects On Coronary Microcirculation in Percutaneous Coronary Intervention**

**Columbia University Medical Center and Cardiovascular Research Foundation**

**Principal Investigator: [name]**

**Scientific basis/Rationale:** The presence of heavily calcified coronary lesions necessitates the use of ablative devices that aid in successful percutaneous coronary intervention (PCI). However, atherectomy devices generate microparticles that embolize to the distal coronary microcirculation and may compromise myocardial tissue perfusion. We hypothesize that the orbital atherectomy system (OAS), a newer generation atherectomy device, reduces the incidence of microcirculatory compromise as compared to older generation rotational atherectomy (RA) due to differences in the mechanism of athero-ablation.

Two mechanisms that deserve particular attention are the eccentric mounting of the OAS crown and the higher flow rates on the vasodilator flush. Firstly, as opposed to rotational atherectomy where the larger, centrally mounted burr may cause obstruction of flow during the atherectomy, the smaller eccentrically mounted crown in OAS allows continuous perfusion during both atherectomy as well as rest periods. Second, both during rest and atherectomy, the flow rates of vasodilatory flush is higher in OAS compared to RA. Combined, these differences in coronary and vasodilator flush flow could lead to improved perfusion of the distal circulation, particularly during the atherectomy runs when risk of embolization is highest.

The loss of microcirculatory function can be transient, with partial or complete restoration of microcirculatory blood flow, or permanent. As shown in studies of patients with acute coronary syndromes, the loss of microcirculatory function is a critical and independent predictor of myocardial recovery and adverse outcomes. The putative protective effects of OAS on coronary microvasculature may therefore be of major clinical significance and impact.

**Central hypothesis:** OAS is associated with lower loss of coronary microcirculatory function as compared to RA.

**Primary Objectives:** To compare the effect of OAS versus RA on coronary microcirculatory function as measured by saline transit time under basal and hyperemic conditions in patients with clinical indication for PCI in whom atherectomy for optimal PCI is clinically warranted.

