#### Preliminary results:

Table 1. Physiological findings\*

	OAS (n=6)	RA (n=4)	P
Post-atherectomy			
Coronary Flow (1/s)	1.78±.21	1.41±.62	0.25
Index of microcirculatory resistance (a.u)	21±6	31±7	0.04
Coronary wedge pressure (mmHg)	21±6	27±6	0.15

± standard deviation; \*preliminary nonrandomized data.

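### The change in wedge pressure across adenosine measures the reversible part of plugging, not the plugging that atherectomy caused, and has no clear reading between devices

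*Combined protocol and SAP*

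**What the plan says.** The section on Coronary Wedge Pressure fixes the timing: "Measurements will be taken immediately following atherectomy and then repeated following administration of adenosine and a 3 minute rest period". It then gives the read-out: "The difference between the pre and post adenosine coronary wedge pressure will be indicative of the microcirculatory" plugging caused by atherectomy. It does not say whether a larger difference is worse, or which device a larger difference would favour.

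The next paragraph of that section states a two-part hypothesis. The first part is "If the effects of OAS on the microvasculature are less than RA". The second is that "the relatively smaller microparticles generated by OAS are more readily" cleared from the microcirculation under adenosine. The prediction drawn from it concerns transit time and Pd × Tmn; Pw is not named.

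The Scientific basis/Rationale recognises that damage may not clear: "The loss of microcirculatory function can be transient, with partial or complete restoration of microcirculatory blood flow, or permanent".

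The footnote to the schedule table, under (5) FFR, includes wedge pressure among the measurements that "will be taken before and immediately after atherectomy and at the end of PCI". A reading before atherectomy is therefore listed there, although the wedge section does not mention one and the stated read-out does not use one.

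Table 1 in Preliminary results reports the absolute level after atherectomy, in the row "Coronary wedge pressure (mmHg"): 21±6 with OAS (n=6) and 27±6 with RA (n=4), P=0.15, nonrandomised. It gives neither a baseline nor a post-adenosine value.

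**The concern.** A before-and-after difference measures what changed between the two readings. Here atherectomy precedes both, so what changed is recovery and not injury. A patient whose microvessels are durably blocked and a patient with no blockage would both show little or no difference.

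The comparison between devices has a further difficulty. Less plugging makes the difference smaller, and easier washout makes it larger. If OAS has both properties, the sign of the OAS-minus-RA contrast is not determined by the hypothesis. Because no direction is stated in advance, a result either way could be presented as support for OAS: a small difference as little plugging, a large one as good washout. The wedge difference is the one measurement that the section ties explicitly to plugging, so its meaning should be settled before data are seen.

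**Working it through.** The plan states no design figure for wedge pressure, so there is nothing to reproduce. The check is algebra, followed by an illustration.

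**Inputs from the protocol**
- Both Pw readings follow atherectomy (Coronary Wedge Pressure).
- Hypothesis: less effect and easier washout with OAS (same section). No sizes are given.
- Loss may be permanent (Scientific basis/Rationale).
- Pilot Pw after atherectomy: 21 (OAS) and 27 (RA) mmHg (Table 1).

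**Inputs assumed, because the protocol does not give them**
- U, the Pw without plugging, taken as equal in both arms: 5 to 20 mmHg.
- f, the share of the plugging-related rise that resolves between the two readings, by adenosine washout, vasodilation of affected vessels or spontaneous recovery during the rest.

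**Model.** Let T be the rise in Pw due to plugging.
- First reading: U + T
- Post-adenosine reading: U + (1 − f)T
- Difference: D = fT
- Residual plugging: (1 − f)T

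U cancels, and D is the part that resolved. If adenosine also shifts Pw by an amount h unrelated to plugging, D = fT + h.

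**Permanent plugging.** With f = 0, D = 0 (or h) for every value of T. This needs no assumed figure.

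**Ranking of the devices.** With h equal in both arms, D is larger for OAS when f(OAS) × T(OAS) > f(RA) × T(RA), that is, when f(OAS)/f(RA) > T(RA)/T(OAS). Taking T as the pilot Pw minus U:

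| Assumed U (mmHg) | T, OAS = 21 − U | T, RA = 27 − U | f ratio above which the ranking reverses |
|---|---|---|---|
| 5 | 16 | 22 | 22/16 = 1.38 |
| 10 | 11 | 17 | 17/11 = 1.55 |
| 15 | 6 | 12 | 12/6 = 2.0 |
| 18 | 3 | 9 | 9/3 = 3.0 |
| 20 | 1 | 7 | 7/1 = 7.0 |

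**Three worked cases (f assumed)**
- U = 10, f = 0.8 (OAS) and 0.3 (RA): D = 0.8 × 11 = 8.8 against 0.3 × 17 = 5.1, so OAS has the larger difference. Yet T is 11 against 17, and the residual is 0.2 × 11 = 2.2 against 0.7 × 17 = 11.9. Both favour OAS.
- U = 10, f = 0.5 in both arms: D = 5.5 against 8.5, so the ranking is correct.
- U = 18, f = 0.8 and 0.3: D = 0.8 × 3 = 2.4 against 0.3 × 9 = 2.7. The ranking is still correct, because 0.8/0.3 = 2.67 is below 3.0.

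Reversal is therefore possible and depends on quantities that the trial does not know in advance.

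**The case against.** The case on the other side has six parts.

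- **No direction is assigned.** A reader might infer that the protocol would score OAS as the more plugged device. It would not, as written: it calls the difference indicative of plugging and does not say that larger is worse. This stands. The defect is an undefined reading, not a specified inverted one.
- **The washout hypothesis is not stated for Pw.** It predicts differences in Tmn and Pd × Tmn. This stands, so the opposing-directions argument is conditional on its carrying over to Pw. The permanent-plugging argument does not depend on it.
- **Wedge pressure is supplementary.** A reader might infer that the trial cannot answer its objective. The documents do not support that. The primary objective rests on saline transit time, the primary indices are FFR, CFR and IMR, and the sample size is based on IMR.
- **Permanent injury is not lost to the trial.** The separate Pw readings carry it, and so does IMR at three time points. Only the derived difference drops it.
- **More than debris clearance enters the difference.** Vasodilator effects and recovery during the rest may contribute, so it is not purely adenosine washout, and zero for permanent plugging is approximate. This stands, but it makes the index less specific and does not rescue it.
- **The raw reading after atherectomy is not a clean alternative.** It contains the unplugged level: if U is 15 to 20 mmHg, that is 15/21 = 71% to 20/21 = 95% of the OAS pilot value. This stands, and is why the fix uses a change from baseline.

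**Conclusion.** The point holds in a limited form. The difference across adenosine reflects the reversible part of any plugging, plus whatever else adenosine and the rest change. It is about zero for permanent plugging, which the Rationale says can occur. That conclusion rests on the timing of the two readings and an additive model, not on any assumed figure.

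Between devices, if the washout hypothesis extends to Pw, the difference has no clear interpretation and may rank the less plugged device as worse. The threshold of about 1.4 to 7 for the washout ratio illustrates this only. It uses an assumed unplugged Pw of 5 to 20 mmHg and a nonrandomised pilot of 6 and 4 patients with P=0.15. The documents do not show that reversal is likely, and with equal washout the ranking is correct. What is at stake is the interpretation of one supporting index.

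**What to change.** In the section on Coronary Wedge Pressure, replace the read-out sentence with three definitions:
- **Plugging:** change in Pw from before atherectomy to the first reading after it, before adenosine.
- **Residual plugging:** change from the same baseline to the post-adenosine Pw.
- **Reversible component:** pre- minus post-adenosine Pw, with a statement that a larger value is not evidence of more plugging.

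Compare the devices on the first two and report the third as description. Settle this before analysis, so that the direction is not chosen after seeing the data.

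The wedge section and the schedule footnote must be reconciled on whether Pw is measured before atherectomy. If it is, as the footnote lists, the change costs only wording. If it is not, compare the first and the post-adenosine Pw levels between the randomised arms, and say that patient-to-patient differences in unplugged Pw add noise. As a guide, with the pilot SD of 6 mmHg and 10 patients per arm (20 in total, allocated 1:1), the standard error of the difference between arms is 6 × √(2/10) = 2.7 mmHg, against a pilot difference of 27 − 21 = 6 mmHg. This fallback needs no added measurement.
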